
Methodology
	
This is a mixed methods study with four arms.
 
 1. Patient questionnaire Patients with Rheumatoid Arthritis cared for at the Barts Arthritis Centre will be asked to complete a questionnaire about Rheumatoid Arthritis and the opportunities/barriers of technology to support care. Questions are a mixture of likert scales and tick box answers 2. Semi-structured patient interviews Patients with Rheumatoid Arthritis cared for at the Barts Arthritis Centre will be invited to participate in a ~60 minute semi-structured interview with a researcher from EECS, which will be recorded and transcribed. The interview will focus on the challenges of living with Rheumatoid Arthritis and the opportunities/barriers of technology to support care. Thematic analysis will be used to analyse qualitative data. 3. Clinician questionnaire E-questionnaires will be distributed via various Rheumatology mailing lists. Questions are a mixture of free text, tick boxes and likert scales, focussing on the opportunities and barriers of technology to support Rheumatoid Arthritis care. 4. Semi-structured clinician interviews Rheumatology Clinicians who agree to participate will be invited to participate in a ~30 minute semi-structured interview with a researcher from EMR, which will be recorded and transcribed. The interview will focus on how clinicians navigate care pathways for Rheumatoid Arthritis and the opportunities and barriers for technology to support care. Thematic analysis will be used to analyse qualitative data. 
Covid-19 sub-study The patients and clinicians who previously participated in an AtTRA interview will be invited by letter (patients) or email (clinicians) to complete a short e-questionnaire to understand whether attitudes to computer supported care have changed in light of the pandemic. Questions are a mixture of free text and likert scales.

Objectives / aims
	
The aim of this work is to determine the opportunities and barriers for intelligent mobile technology to support Rheumatoid Arthritis Care, targeted at both patients and clinicians as end users. To this end, the study seeks to

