4.2. Secondary objective

1. Do the perceived opportunities and challenges vary according to patient demographics e.g. disease activity, disease duration, patient age?
2. What are the challenges of living with Rheumatoid Arthritis? (This will include issues around everyday life, flares, pain, medication and appointments from a patient perspective.)
3. Do the perceived opportunities and challenges vary according to clinician demographics e.g. age, subspeciality?
4. Are there significant differences in patient and clinician expectations for health technology assessed parameters?
5. Have the perceived opportunities and challenges changed since the rapid institution of remote care due to the Covid-19 pandemic?

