Interview studies will end when researchers agree that 'meaning saturation' has been reached; i.e. that further interviews will not add any further new information. Questionnaire studies will end when the specified target numbers have been reached.

7. Statistical considerations

Due to the study type there is no statistical powering for the patient population. Although the majority of the study is qualitative, analysis of the quantitative aspects of the questionnaires will be planned with the support of the Experimental Medicine and Rheumatology Statistician to ensure appropriate statistical methods are used in any and all analyses

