7.1. Sample size

Patient questionnaire:

100

This target sample size has been set based on the sample size of other similar studies(6).

Clinician questionnaire:

40

This target sample size has been set pragmatically, based upon anticipated responses.

Patient interview:

15-25 participants.

The interviews will be analysed using thematic analysis, which advises stopping data collection when no new information is being gathered. Based upon the literature, “meaning saturation”, when researchers have a full understanding of all aspects of the topic tends to occur between 16-24 interviews⁽⁷⁾.

Clinician interview:

10-15 participants.

As above, the interviews will be analysed using thematic analysis. However, in this case a smaller sample size has been chosen, as the pool of potential participants is smaller. Additionally, we anticipate a smaller number of interviews to be required to reach “meaning saturation” as the interviews will be conducted by a Rheumatology clinical research fellow, and knowledge of the researcher has been demonstrated to reduce the required sample size⁽⁸⁾.

Covid-19 sub-study:

15-25 participants (Patients and Clinicians combined). This target sample size has been set based upon an anticipated $\approx 50\%$ response from previously interviewed participants

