7.2. Method of analysis

Quantitative Analysis

Descriptive statistics will be predominantly used to analyse the quantitative sections of the questionnaires. However, if no clear trends are identified then further statistical analysis is likely to include the following:

- One sample t-tests will be used for Likert scales to compare the mean of scores with the central value of the score
- Chi-square or Fisher’s exact test to assess the associations between patient groups stratified according to demographic parameters
- Comparison of quantitative variables, two sample t-tests and nonparametric Mann-Whitney tests will be applied
- Multivariate analysis by binary logistic regression to examine the variables influencing the willingness to use technology.

Qualitative Analysis

Interviews will be transcribed and analysed using thematic analysis, with the assistance of coding software. This involves first reading and re-reading the transcripts to gain familiarity with the data; iterated coding leading to the

generation of overarching themes from patterns emerging from the data; reflection on and definition of the themes and how they contribute to an understanding of the data; and finally the writing of a thick description of the data. Free-text questions from questionnaires will be analysed in the same manner. To increase reliability coding will be done by both a clinician and computer scientist who will monitor and discuss themes emerging throughout the process.

8. Ethics

This study will be carried out in accordance with the ethical principles in the Research Governance Framework for Health and Social Care, Second Edition, 2005 and its subsequent amendments as applicable, and applicable legal and regulatory requirements.

Summary of Main Issues

- Confidentiality and Data Storage:

Data will be stored in compliance with Data Protection Act. All data will be pseudo-anonymised where data of birth and initials will be linked to a unique participant identifier for the patient in an encoded fashion.

- Interview Transcription:

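### Chi-square tests on strata of age, disease duration and disease activity are an inefficient way to address secondary objective 1 with 100 patients; keep these factors continuous and the Likert responses ordered

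*Protocol*

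**What the plan says.** Secondary objective 1 (Protocol 4.2) asks: "Do the perceived opportunities and challenges vary according to patient demographics e.g. disease activity, disease duration, patient age". The three examples of demographics are thus disease activity, disease duration and age.

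Protocol 7.2, repeated in the synopsis row on statistical methodology, makes the quantitative analysis mainly descriptive and then adds: "However, if no clear trends are identified then further statistical analysis is likely to include the following". Of the four items that follow, three bear on objective 1:

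- a contingency-table method (chi-square or Fisher's exact), whose stated purpose is "to assess the associations between patient groups stratified according to demographic parameters";
- two-group tests of measured variables, by t-test or by Mann-Whitney;
- a regression model for willingness, which the section words as "Multivariate analysis by binary logistic regression to examine the variables influencing the willingness to use technology".

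The remaining item, a one-sample t-test of Likert scores against the scale midpoint, involves no patient factor.

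The synopsis describes the patient questionnaire as follows: "Questions are a mixture of likert scales and tick box answers". Section 7.1 sets the patient questionnaire at 100, by precedent from similar work, and Section 7 states: "Due to the study type there is no statistical powering for the patient population". Sections 6 and 10.1 have disease duration and current disease activity recorded for each patient, and 10.1 adds age and ethnicity.

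**The concern.** Age, disease duration and a disease activity score are measured on a scale. Testing them as strata in a contingency table discards that scale, and an ordinary chi-square test also ignores the order of a Likert response. If willingness to use technology is asked on a Likert scale, binary logistic regression collapses that order too. Section 7.2 lists no correlation, trend test or ordinal model that would avoid both losses.

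The patient sample is small and its target is fixed by precedent. Under 7.2 the tests come into play when description shows no clear trend, which is where associations are likely to be modest and low power matters most. A non-significant table could then be read as evidence that perceptions do not vary with age, duration or activity, when an analysis of the same data on its original scale would have had a better chance of showing the association.

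**Working it through.** **No plan figure to reproduce.** The protocol states no power, significance level, effect size, number of strata or cut-points. What follows sizes the loss under stated assumptions.

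**Input from the protocol:** n = 100 patients (7.1).

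**Assumptions, not in the protocol:** two-sided 5% level; five-level response; factor standardised and normally distributed; median split; odds ratio per SD of 1.65 or 1.82.

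**Step 1: information kept by a split, near the null.** Splitting a normal variable at quantile q keeps φ(z_q)² / [q(1−q)] of the information.

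- Median split: 2/π = 0.637, so 36% is lost and 100 patients count as about 64.
- 30/70 split: 0.576, 42% lost.
- 25/75 split: 0.539, 46% lost.
- 20/80 split: 0.490, 51% lost.
- Both variables split at the median: (2/π)² = 0.405, 59% lost, effective n about 41.
- Tertiles scored as a trend: 0.793 kept, 21% lost. A plain chi-square test does not use that trend.

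**Step 2: simulated power at n = 100.** The response is a logistic latent variable cut into five levels. Relative loss = 1 − (power of the method) / (power of the ordinal score test).

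| Method | OR 1.65 per SD | Loss | OR 1.82 per SD | Loss |
|---|---|---|---|---|
| Chi-square 2×5, median split | 36% | 1 − 36/78 = 54% | 49% | 1 − 49/91 = 46% |
| Chi-square 2×2, both dichotomised | 46% | 1 − 46/78 = 41% | 62% | 1 − 62/91 = 32% |
| Mann-Whitney, median split | 57% | 1 − 57/78 = 27% | 72% | 1 − 72/91 = 21% |
| Binary outcome, continuous factor | 64% | 1 − 64/78 = 18% | 79% | 1 − 79/91 = 13% |
| Proportional-odds score test, continuous factor | 78% | reference | 91% | reference |

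A separate run of the same design, without the binary model, gave 35%, 51%, 58% and 77% at the smaller odds ratio and 49%, 63%, 73% and 90% at the larger. Its chi-square losses run from 1 − 63/90 = 30% to 1 − 35/77 = 55%, and its Mann-Whitney losses from 1 − 73/90 = 19% to 1 − 58/77 = 25%. Type I error was about 5% for all four methods.

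**Step 3: a different model as a check.** Here the latent variables are bivariate normal with correlation r, the five levels have unequal frequencies, and Spearman's test on the ungrouped factor is the reference.

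| Method | r = 0.2 | r = 0.3 | r = 0.4 |
|---|---|---|---|
| Spearman, ungrouped factor | 0.46 | 0.81 | 0.96 |
| Chi-square 2×2 | 0.27 (−41%) | 0.51 (−37%) | 0.76 (−21%) |
| Chi-square 3×2 (tertiles) | 0.23 (−51%) | 0.47 (−42%) | 0.75 (−22%) |
| Binary logistic, continuous factor | 0.37 (−19%) | 0.68 (−15%) | 0.92 (−5%) |

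At r = 0.3, a 3×5 chi-square gives 0.39 (−52%) and Mann-Whitney on a median split 0.62 (−23%). Using tertiles does not rescue the chi-square test, and every loss shrinks as the association strengthens.

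**The case against.** The strongest reply is that these tests are provisional. They are conditional on description showing no clear trend, they are only likely to be used, the study is declared unpowered, and Section 7 says the quantitative analysis will be planned with a statistician. Cut-points and covariate coding normally belong in an analysis plan. This stands in part: the absence of cut-points is not the finding, and the protocol does not say when they would be chosen. It does not remove the point, because 7.2 names its methods and the named test for stratified groups is a weak one for the factors in objective 1.

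A second reply is that other listed methods avoid part of the loss. This stands. A t-test or Mann-Whitney test of age between yes and no responders to a tick box keeps age continuous; a Mann-Whitney test of a Likert item between two groups keeps the response order. The logistic regression item does not say that covariates are grouped. None of these, however, keeps a continuous factor and an ordered response together.

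Third, the cutting of these three factors is inferred. Section 7.2 speaks only of demographic parameters; 4.2 supplies the examples. The inference is natural but not explicit, and for a categorical factor such as ethnicity, also collected, chi-square is suitable.

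A reader might go further and infer that the whole plan for objective 1, including the willingness model, forfeits a third to half of its power. The documents do not support that. The logistic model loses much less, the scale of the willingness item is not stated, and any figure rests on effect sizes and a split that the protocol does not give.

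**Conclusion.** The point holds for the chi-square and Fisher's exact route when it is applied to age, disease duration or disease activity. Under the Step 2 assumptions, that route loses roughly 30 to 55% of the power of an ordinal model with a continuous factor. The loss is about 20 to 27% for the listed Mann-Whitney test on a median split, and about 13 to 19% for binary logistic regression with continuous covariates if willingness is a Likert item, the upper end coming from r = 0.2 in Step 3. If willingness is yes/no, the logistic model loses nothing. With a strong association the losses are smaller, for example 21% for a 2×2 chi-square and 5% for the logistic model at r = 0.4.

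This is a worthwhile improvement to a secondary, conditional analysis. It does not affect the primary endpoint, which is thematic, and the protocol makes no power claim that it would overturn.

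**What to change.** In Protocol 7.2, and in the matching synopsis row, state that if inferential tests are run for secondary objective 1:

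- age, disease duration and disease activity enter as continuous variables;
- Likert items, including willingness if it is one, are analysed by proportional-odds regression or, for a single factor, a rank correlation;
- true yes/no items are analysed by binary logistic regression with the same continuous terms;
- chi-square or Fisher's exact tests are kept for truly categorical factors such as ethnicity;
- strata of the continuous factors are used only for descriptive display.

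The cost is wording: no extra patients, data or visits. The small downside is reliance on the proportional-odds and linearity assumptions, both of which can be checked.

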8.1. Annual Safety Reporting

There are no safety considerations for patients enrolled in this study. Their care while taking part in AtT-RA is according to national standards as outlined by NICE. There are no additional interventions that would pose a risk to the patient.

9. Public involvement

There has been an open dialogue with the MATURA PPI group from the outset of the project. Draft questionnaires and semi-structured interviews were sent to members of the Rheumatoid Arthritis PPI group for feedback. Practice interviews were conducted with volunteers to sense-check and time interviews, with modifications made based on participant feedback.

10. Data handling and record keeping

10.1. Data management

Paper Questionnaire

The questionnaire itself will act as the source data. These will be anonymised, labelled only with participant's unique study number. Once completed questionnaires are returned, data on the patient's demographic and clinical information (including age, ethnicity, disease duration; current disease activity; current and previous DMARDs) will be collected and recorded on a pseudo-anonymised excel spreadsheet using only patient's unique study number. A separate electronic database will match the patient's unique study number to their hospital number. All electronic databases will be stored within the EMR drive on Barts Health Trust Network, with access restricted to those directly involved in EMR research team.

E-Questionnaire

The e-questionnaire itself will act as the source data. These will be anonymised and labelled only with the participant's unique study number.

Semi-Structured Interview Data

Interview participants will complete a short questionnaire including technology usage and limited demographic information at the end of the questionnaire. Following completion of the interview, data on the patient's demographic and clinical information (including age, ethnicity, disease duration; current disease

activity; current and previous DMARDs) will be collected and recorded on a pseudo-anonymised excel spreadsheet using only patient's unique study number/paper record form.

Interviews will be recorded on two audio devices (one to act as back-up in the event of the first failing), and transcribed by an external company (Bristol Transcription Services). Participants' identity will be confirmed at the start of interview, prior to commencement of audio-recording. Once audio-recording has commenced only the participants' unique study number will be used. The audio recordings will be deleted once transcription is complete. Transcripts will be labelled with the participant's unique study number and no other patient identifiable information will be included. Transcripts will be analysed and coded at EECS. Once analysis is complete the transcripts will be stored within a secure locked room within the Department of Experimental Medicine and Rheumatology.

10.2. Source Data

The completed paper and e-questionnaires will be the source data for this arm. Completed transcripts will act as source data for the interview studies. Clinical and Demographic data will be collected in an anonymised electronic spreadsheet kept within the EMR drive on Barts Health NHS Trust Network. Following analysis these will be stored within a secure locked room within the Department of Experimental Medicine and Rheumatology.

10.3. Confidentiality

Audio recording will not include participant's names or other overtly patient identifiable data to ensure confidentiality at the point of transcription. Questionnaires will be assigned a unique study number with no further identifiable information.

Data will be stored in compliance with Data Protection Act. All data will be pseudo-anonymised where data of birth and initials will be linked to a unique participant identifier for the patient in an encoded fashion.

10.4. Record retention and archiving

During the course of research, all records are the responsibility of the Chief Investigator and must be kept in secure conditions. From the end of the study, it is a requirement of the Research Governance Framework and QMUL Policy that all records are kept for a further 20 years. Electronic data will be stored and archived for 20 years in compliance with QMUL archiving SOP in encoded password protected format. The data collected and generated as part of this study's objectives will be analysed at the School of Electronic Engineering and Computer Sciences, Queen Mary University of London, and

following analysis will be stored in the Centre for Experimental Medicine and Rheumatology.

11. Safety reporting

Due to the nature and design of this study, safety reporting of adverse events will not occur.

12. Monitoring and auditing

Monitoring activities will be commensurate to the risk of the study. As this is a low-risk study “on site monitoring” will not be required but a triggered visit may occur if warranted, or may be arranged as a part of the Centre for Experimental Medicine & Rheumatology ongoing quality management system procedures. Such on-site monitoring activities would include data verification checks against patients’ medical notes to monitor the accuracy of the data being collected. For a study of this nature, central monitoring activities will be more appropriate and this will be developed as a part of a central data management plan to monitor timely transfer of study data to the study database, review of completeness and accuracy of the data, and to look for any anomalies or unusual patterns in the data that prompt and ‘on-site’ monitoring visit. The Sponsor or delegate retains the right to audit any study, study site or central facility. In addition, any part of the study may be audited by the funders where applicable.

13. Study committees

As the study is classified as low-risk, the study will be overseen by a Trial Management Group Committee. This will consist of the Chief Investigator, Co-investigator(s), study manager, research nurse, other clinical team staff, database manager.

The committee will meet to review data collection and will be responsible for the day-to-day running of the study and overseeing implementation of the protocol. The committee will meet monthly at a time and date dictated by the Chief Investigator and a copy of all agendas, papers and minutes shall be stored in the Trial Master File.

14. Finance and funding

This project is funded through the EPSRC funded PAMBAYESIAN grant (EP/P009964/1) procured by the School for Electrical Engineering and Computer Science, within Queen Mary University of London. The project has been designed and developed by staff working within the School for Electrical Engineering and Computer Sciences and the Centre for Experimental Medicine and Rheumatology.

15. Insurance and indemnity

The insurance that Queen Mary University of London has in place provides cover for the design and management of the study as well as "No Fault Compensation" for participants, which provides an indemnity to participants for negligent and non-negligent harm.

16. Dissemination of research findings

The results of the AtTRA study will be disseminated at different levels. Firstly, the results will be presented to researchers within the PAMBAYESIAN project to inform the design of prototype technology interfaces. The results of the project will be disseminated amongst local patient groups including the local National Rheumatoid Arthritis Society patient group (<https://www.nras.org.uk/groups/east-london-nras-group>). Research findings from the AtTRA study will form a significant part of the M.D. thesis of a EMR research student, and be disseminated Nationally/Internationally, through routine publishing in academic journals, and presentation at conferences, e.g. European League Against Rheumatism (EULAR) & American College of Rheumatology(ACR), either as speaker or poster.

17. References

1. NHS England (2019). NHS long term plan. Available from: <https://www.longtermplan.nhs.uk/wp-content/uploads/2019/01/nhs-long-term-plan.pdf>
3. Luo, Dee; Wang, Penny; Lu, Fengxin; Elias, Josephine,; Sparks, Jeffrey A; Lee, Yvonne C. Mobile Apps for individuals with Rheumatoid Arthritis: A systematic review. *J Clin Rheumatol*. 2018 Jun 21.
